Power calculations for Aims 1 and 2 were updated to harmonize with the final analysis plan and the realized recruitment, which had a slight reduction in patient-level sample size (from 240/240 control/treatment to 222/221 control/treatment, given that the stepped-wedge study design wave rollover rules were not dependent on intervention assignment). The overall design is retained (relative to the submitted proposal) and the power numbers remain robust. Notably, surgeon-level sample size has not changed, and it is this sample size that is primarily driving the power. We have not modified the assumption that the between-surgeon variance accounts for 30% of the total variance. As noted previously, this is conservative considering preliminary data suggests this variance is as low as 5%.

Under our modified plan, there are four endpoints in Aim 1, the four question types. In this case, tests will be conducted with nominal $\alpha=0.05/4 = 0.0125$. Supported by our preliminary data, we assume a worst-case scenario of 65% of control patients will be in the non-activation set (the zero category). We consider an odds-ratio of improved category (moving to a higher category of questions asked) in the treatment (relative to control) of 1.3. Under these settings, we have 85% power to detect a treatment difference in [Q-Advance Directives]. For each of the other three categories, we have over 93% power to detect a difference. Under our modified protocol, regret is the only endpoint in Aim 2. In this case, testing will be conducted with nominal $\alpha = .05$. We assume the upper bound risk of regret is 0.3; we will have over 91% power to detect a regret risk difference of 0.23.

This additional analysis of our primary endpoints is otherwise unchanged from our per-protocol plan. Our modified analysis will compare the effectiveness of the QPL intervention relative to usual care on patient engagement. We will use an intention to treat (ITT) analysis using all available data from participants based on group assignment. The intervention effect will be tested in the framework of generalized linear mixed effects models with a treatment dummy variable, surgeon random effect and site-by-time dummy variables to control site-specific secular trends. Again, we will consider four specific types of questions and evaluate them with ordinal categories:

- Number of OPTIONS questions asked by patients and family members (0, 1, 2+)

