DESIGN, SETTING, AND PARTICIPANTS A Patient and Family Advisory Council (PFAC) was created to help identify preoperative decisional needs. The PFAC included 4 men and women who had previous experience with high-risk surgery as older patients or their family members; the PFAC met monthly at a local library from May 2014 to April 2015 to examine findings from a prior qualitative study and to integrate themes with PFAC members' experiences. Patient observations included 91 recorded conversations between patients and surgeons and 61 patient interviews before and after surgery. The PFAC members and other stakeholders evaluated 118 publicly available questions and selected 12 corresponding to identified needs to generate a question prompt list (QPL). Three focus groups, including 31 community members from diverse backgrounds, were conducted at community centers in Madison and Milwaukee, Wisconsin, to refine the QPL. A clinical pilot with 42 patients considering surgery was conducted in one outpatient surgical clinic in Madison.

MAIN OUTCOMES AND MEASURES Generation of a QPL to address patients' preoperative informational and decisional needs.

RESULTS Through exploration of qualitative data, the PFAC noted 3 critical problems. Patients and family members believed surgery had to be done, were surprised that postoperative recovery was difficult, and lacked knowledge about the perioperative use of advance directives. The PFAC identified a need for more information and decisional support during preoperative conversations that included clarification of treatment options, setting postoperative expectations, and advance care planning. The following 3 question prompt categories arose: "Should I have surgery?" "What should I expect if everything goes well?" and "What happens if things go wrong?" The final list included 11 questions within these domains, was understandable in English and Spanish, and was acceptable to patients in the clinic.

CONCLUSIONS AND RELEVANCE Through direct engagement of stakeholders, a QPL was created to address core decisional and informational needs of surgical patients. Future testing will evaluate whether this list can be used to improve patient engagement and reduce postoperative regret and conflict about postoperative treatments.

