- “How will this surgery affect my other health problems?” and
- “After I leave the hospital, what type of care do you think I will need?”

Complications

The PFAC reviewed qualitative data that exposed a wide variation in treatment preferences for serious postoperative complications. Patients believed the surgeon knew their wishes despite the lack of explicit discussion. For example, 1 study patient stated, “The only thing I don’t want, if I do die, I don’t want to be revived.” This type of information was not discussed with surgeons. A few patients mentioned their advance directive, but the surgeon did not explore their preferences further. Thus how to proceed in the event of a postoperative complication was unclear. Some believed family members were familiar with their preferences and could make decisions if needed.

The PFAC members were concerned that patients needed more advance care planning. They expressed dismay that patients’ treatment preferences were not communicated: “There is a disconnect between what the patients want and who is the right person to tell these wishes.” The PFAC struggled to understand how specific directives might need to be tailored to the surgical setting and were shocked by the lack of standard procedures for notifying all health care professionals about existing directives. They identified a critical need for patients to clarify their preferences with the surgeon and to discuss how directives might be interpreted during the perioperative period.

The PFAC sought questions to promote conversation about “What happens if things go wrong?” They chose the following question prompts to encourage this type of discussion:

- “Can you describe serious complications and explain what those might mean for me?”
- “If I’m too sick to speak for myself, how can I make sure you know my wishes?” and
- “If I decide to appoint someone to make medical decisions for me, what do I need to do to make those arrangements official?”

Acceptability of the QPL

English- and Spanish-speaking community members endorsed the questions on the QPL and believed that they could ask all the questions on the list. Surgeon stakeholders agreed they could answer the questions.

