For surgeons, this intervention will require translating professionally defined notions of risk and benefit into patient-centered outcomes, specifically goals and expectations. Pecanac et al²³ have previously documented that surgeons skillfully describe the gravity of high-risk surgery and routinely disclose risk, yet we find it remarkable that this process inadequately supports patients as they decide whether to have surgery or prepare for expected outcomes. Although sur-

Figure 2. Patient and Family Advisory Council Question Prompt List Brochure

geons work hard to provide critical information, the meaning of *big surgery* and *risk of heart attack* is unfamiliar to patients and families who struggle to imagine how such events may be experienced. Rather than more information, they need more interpretation of the information surgeons currently provide.³³ The QPL questions are framed to help patients access surgeons' knowledge in a way that patients can understand.

For patients, the QPL aims to promote informed decision making by supporting inquiry with questions they would not have thought to ask. Traditional models of clinical decision making theorize that patient preferences for decisional control are unique and decision dependent; some prefer complete physician control whereas others want equally shared decisions or complete control.^{34,35} Newer theoretical models propose that most patients want to be involved but simply do not know how.¹⁴ This problem can be mediated by previsit edu-

cation or coaching with interventions such as the QPL. Because the patient experience is transactional (ie, determined by the actions of surgeons and patients),³⁶ patients who are motivated to be involved are more likely to participate in collaborative decision making.

Although many versions of questions to ask physicians exist, they contain questions that patients ask spontaneously. In our observation, surgeons regularly inquire whether patients have questions and patients respond with logistic or technical concerns, such as "Can my wife sleep in my room?" and "Will you use stitches or staples?"²³ Although these concerns are important to patients, they do little to engage patients in a discussion about trade-offs or to set realistic expectations for what life might be like after surgery. The QPL addresses specific needs that are not routinely queried by patients and families.

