For each quantitative aim, we desire a family-wise two-sided type I error rate of $\alpha=0.05$; under a Bonferroni correction, tests will be conducted with nominal $\alpha=0.05/2=0.025$ because there are two primary endpoints for aim 1 and aim 2 (table 2). Using patient satisfaction data at one site, we found that between-surgeon variance accounts for only 5% of the total variance. Because power in the stepped wedge design is slightly degraded with greater variance between (vs within) surgeons, we assumed a worst-case scenario between-surgeon variance of 30%. We interpreted this as the interclass correlation between multiple patients of the same surgeon at a given site and included a surgeon-level random effect in our calculation, anticipating between 5% and 30% of the total variance to be accounted for by surgeon effects (ie, interclass correlation (ICC) =0.05–0.30). Extending the information-based method of computing power for a basic stepped wedge design⁴⁹ to the case of our multisite stepped wedge design, we custom-programmed power calculations using R V.3.2.1 (R Foundation for Statistical Computing).

With this method, we computed power of 82% to detect small-to-medium and 93% to detect medium effect sizes of Cohen's $d=0.425$ and $d=0.5$, respectively. Assuming the SD for PEPPI-5 within each treatment arm is 4.3,⁶⁴ we will have 93% power to detect effects as small as 2.15 points. For the number of patient questions, we assumed a mean difference of 1.4 questions between arms.⁴⁰ Assuming overdispersion of two relative to Poisson data, within arm SD=2.7, yielding $d=1.4/2.7=0.52$, which we are well powered to detect. For the MYCaW well-being scale, Jolliffe *et al*⁶⁵ found SD=1.26 at 6 weeks, and a 6-week versus baseline mean difference of 0.59. We will also have 93% power to detect an MYCaW difference as small as $0.5\times1.26=0.63$, comparable with the difference over time in Jolliffe *et al*.⁶⁵ For regret, we assume the upper bound risk of the presence of regret is 0.3,⁵⁵ yielding SD=0.46; we will have over 90% power to detect a regret risk difference of 0.23. Nearly identical power results were obtained via a continuous latent liability model for a binary event (regret).⁶⁶ To account for clustering within sites, this

calculation includes fixed effects terms for site, time (wave) and site-by-time, reflecting our a priori analysis plan.

Qualitative analysis

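### The 65% zero share is not shown to be a worst case for Advance Directives questions, so the 85% power printed for that endpoint is unsupported

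*Combined protocol and SAP*

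**What the plan says.** The SAP section on further analysis of primary endpoints, under the updated analysis plan and modified power analysis, gives one control-group input for the four Aim 1 question types: "we assume a worst-case scenario of 65% of control patients will be in the non-activation set (the zero category"). It says that this is supported by preliminary data, which it does not show. The effect is an "odds-ratio of improved category (moving to a higher category of questions asked) in the treatment (relative to control) of 1.3", and "tests will be conducted with nominal $\alpha=0.05/4 = 0.0125"$. The result is "Under these settings, we have 85% power to detect a treatment difference in [Q-Advance Directives"], with over 93% for each of the other three types. No zero share is given by type. The Advance Directives outcome is binary (none versus one or more); the other three have three ordered categories.

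The preliminary work is described in the appended QPL development paper. Its abstract states: "Patient observations included 91 recorded conversations between patients and surgeons". On advance care planning it says: "A few patients mentioned their advance directive, but the surgeon did not explore their preferences further". It also reports that patients and families lacked knowledge about using advance directives around surgery. Its Table 2 records the advisory council's view that patients had no opportunity to state clearly their preferences on life support after surgery.

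**The concern.** The zero share is the event-rate input for a binary endpoint. At a fixed odds ratio, power falls as the zero share moves from 65% towards 100%. Calling 65% the worst case for all four types therefore asserts that at least 35% of control visits contain an Advance Directives question. Nothing printed supports that for this type, and the qualitative findings point the other way.

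Advance Directives is one of four Aim 1 primary endpoints, each tested at 0.0125. A reader told that power is 85% under worst-case settings could take a null result as good evidence that the QPL does not prompt advance-care-planning questions. If such questions are rare in usual care, the test may have had little chance of detecting a worthwhile effect.

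**Working it through.** **Inputs.** From the SAP's modified power analysis: 65% zero share, odds ratio 1.3, alpha 0.0125, 222 control and 221 intervention patients, and a surgeon variance share of 30% (as low as 5% in preliminary data). Two-sided testing comes from the published protocol's sample size section ("we desire a family-wise two-sided type I error rate of" 0.05). The crossover schedule is that protocol's Table 1: 40 surgeons, six waves, eight surgeons crossing per wave. Assumed, because no document gives it: Advance Directives zero shares of 80%, 90% and 95%.

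**Method.** Information-based stepped-wedge power with a surgeon random effect and 30 site-by-wave fixed effects. With total variance 1 and m patients per surgeon-wave, each surgeon's six wave means have covariance V = ((1 − ICC)/m)·I + ICC·J. SE is the square root of the treatment element of (ΣZ′V⁻¹Z)⁻¹.

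**Step 1: check the method on the published protocol.** With m = 2 (480 patients), SE = 0.1340 at ICC 0.05 and 0.1305 at ICC 0.30. At alpha 0.025 (critical value 2.241):
- ICC 0.05: d = 0.425 gives Φ(0.425/0.1340 − 2.241) = 82.4%, and d = 0.5 gives 93.2%.
- ICC 0.30: 84.5% and 94.4%.

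The published protocol states 82% and 93%, so the method is close to the sponsor's.

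**Step 2: try the printed 85%.** Now m = 443/240 = 1.846, SE = 0.1388 (ICC 0.05) or 0.1354 (ICC 0.30), and the critical value is 2.498.
- p1 = 0.35; p2 = 0.35 × 1.3/(0.65 + 0.35 × 1.3) = 0.455/1.105 = 0.412.
- d = (p2 − p1)/√(p̄(1 − p̄)), with p̄ = 0.381, is 0.0618/0.4856 = 0.127.
- Power = Φ(0.127/0.1354 − 2.498) = Φ(−1.56), about 6%. A two-proportion test that ignores clustering gives 12.3%.

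The 85% does not reproduce. The effect of the zero share therefore has to be shown at other odds ratios.

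**Step 3: raise the zero share at a fixed odds ratio.** An odds ratio of 2.66 (ICC 0.30) or 2.73 (ICC 0.05) gives 85% at 65% zero. Worked line at 90% zero, ICC 0.30: p2 = 0.1 × 2.659/(0.9 + 0.2659) = 0.228; d = 0.346; 0.346/0.1354 − 2.498 = 0.057; Φ = 52%.

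| Control zero share | OR 1.3 | OR about 2.7 (set to 85% at 65% zero) | OR 3.67 |
|---|---|---|---|
| 65% | about 6% | 85% | 98% |
| 80% | 4-5% | about 76% | 96-97% |
| 90% | 3% | 52-53% | 83-85% |
| 95% | 2% | 28% | 55-57% |

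Ranges cover ICC 0.05 and 0.30. The odds ratio 3.67 is exp(1.3), what 1.3 would mean as a log odds ratio; the documents do not say this was intended. Without clustering, the odds ratio giving 85% at 65% zero is 1.98, and power then falls to 73.5%, 47.3% and 24.2%.

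**Step 4: cross-check with the planned model.** A simulation of the logistic random-intercept model (400 trials per setting, latent ICC 0.30, odds ratio about 2.6) gave 83%, 74%, 50% and 27% at 65%, 80%, 90% and 95% zero, with Monte Carlo error of about 2 points.

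**The case against.** A reader might infer that the preliminary data show Advance Directives questions to be far rarer than 35%. They do not. No document gives a count or share of visits with such a question. The only number tied to preliminary data is the 65% itself. For scale, 35% of 91 conversations is 31.9, but the paper's remark about a few patients carries no denominator and rests on interviews as well as recordings. It also concerns mentions of a directive, whereas the coding manual counts questions under a wider code and includes those from family and friends. The paper's statement that "The QPL addresses specific needs that are not routinely queried by patients and families" describes the whole QPL, not this endpoint.

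A reader might also infer that 85% would stay overstated whatever odds ratio is used. That fails for some inputs: odds ratio 3.67 gives 83-85% at 90% zero, and in the simulation odds ratio 3.0 gives 85% at 80% zero.

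Two further objections are fair. The mismatch between odds ratio 1.3 and 85% is the larger error in the same paragraph, and at 1.3 the base rate hardly matters because power is minimal throughout. Recruitment is also complete, so a new power figure changes no design feature.

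What survives is narrower. One zero share is used for all four types without justification by type, the worst-case label needs a bound that the documents do not supply for Advance Directives, and correcting the odds ratio alone would leave that input in place.

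**Conclusion.** The point holds as one of missing support. For Advance Directives, neither the worst-case label nor the 85% follows from anything in the documents, and the qualitative findings suggest that the true zero share exceeds 65%. How much this matters depends on two unknowns, the zero share and the odds ratio. With an odds ratio of about 2.7, power drops from 85% to roughly half at 90% zero and to 28% at 95%. With 3.67 it stays at or near 85% up to 90% zero and falls to 55-57% at 95%.

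The figures rest on the Table 1 schedule, 443 patients spread evenly over surgeon-waves, and the assumed 80-95% range. The SAP allows up to three patients per surgeon per wave, and the realised spread is not given. The choice of ICC between 0.05 and 0.30 changes little.

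**What to change.** In the modified power analysis:

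1. Delete the worst-case label and the common 65% input.
2. Before unblinding, take the zero share of each question type from the coded transcripts pooled over arms. The SAP already requires coding to finish before unblinding. If the QPL increases asking, the pooled share is a lower bound on the control share.
3. State the odds ratio actually used. Re-running the program with only a new zero share would not repair the mismatch with 1.3.
4. Recompute Advance Directives power for the planned logistic random-effects model at the pooled share and over a range such as 65-95%, and print it in place of 85%. Do the same for the other three types, each with its own share.
5. State that a null Advance Directives result will be interpreted from its confidence interval, and not as evidence of no effect.

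The cost is one set of blinded frequencies, one re-run of the power program and a revised paragraph. Tests, alpha and sample size stay as they are. The downside is that the printed power is likely to be less favourable.

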- Number of EXPECTATION questions asked by patients and family members (0, 1, 2+)
- Number of ADVANCE DIRECTIVES questions asked by patients and family members (0, 1+)

-Number of RISKS questions asked by patients and family members (0, 1, 2+)

Denote each question type with [Q-type], where type is either Options, Expectation, Advance Directives, or Risks. [Q-Advance Directives] is a binary variable, the other three types are three-category ordinal variables. Accordingly, a logistic random effects model will be used to analyze [Q-Advance Directives], while ordinal logistic random effects models will be used for analyzing the other three types.

For Aim 2, there is no change to the modeling approach for regret: we will use a logistic random effects model. We will use an intention to treat analysis using all available data from participants based on group assignment. We will use a logistic random effects model with a treatment dummy variable, surgeon random effect and site-by-time dummy variables to control site-specific secular trends.

Additional considerations: Aim-1 question asking

After performing the ITT analysis, we will restrict the analysis by removing the dyads (patient and family member) where major surgery was not discussed or the patient did not have a vascular or oncologic problem. This is based on the T0 transcript of the conversation with the surgeon, which confirms whether the patient discussed surgery with the surgeon and had a vascular or oncologic problem. Specifically, we will use the subgroup analysis document, coded by the primary coder and confirmed in group consensus, to identify enrolled patients for whom surgical treatment was not discussed, or on evaluation after enrollment, the patient did not make entry criteria to be in the study, specifically, the patient did not have a diagnosis of cancer or vascular disease.

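### The Aim 1 power figures (85% and over 93%) do not fit the stated odds ratio of 1.3; at that odds ratio power is at most 12–13%, and about 4–6% under the planned models

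*Combined protocol and SAP*

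**What the plan says.** The SAP section *Updated analysis plan and modified power analysis* leaves four Aim 1 primary endpoints, each tested at 0.05/4 = 0.0125. The realised sample is 222 control and 221 intervention patients. It assumes that 65% of controls ask no question of the given type and that surgeons account for 30% of the total variance.

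- Effect size: "We consider an odds-ratio of improved category (moving to a higher category of questions asked) in the treatment (relative to control) of 1.3".
- Binary endpoint: "Under these settings, we have 85% power to detect a treatment difference in [Q-Advance Directives".
- Ordinal endpoints: "For each of the other three categories, we have over 93% power to detect a difference".
- Overall: "The overall design is retained (relative to the submitted proposal) and the power numbers remain robust".

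For the analysis, Advance Directives gets a logistic random-effects model, and "ordinal logistic random effects models will be used for analyzing the other three types". Each model has a surgeon random effect and site-by-time dummies. The SAP gives no other effect size for these four endpoints under the modified plan.

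**The concern.** An odds ratio of 1.3 on a 35% base is a small effect, and 443 patients at alpha 0.0125 are few for it. Two other statements about the same design give the contrast. For regret, the same paragraph says "we will have over 91% power to detect a regret risk difference of 0.23", which is a difference almost four times as large (0.23/0.062 = 3.7) tested at a looser alpha of 0.05. In the appended published protocol, *Sample size and power calculation*, "we computed power of 82% to detect small-to-medium and 93% to detect medium effect sizes of" Cohen's d = 0.425 and 0.5, with 480 patients and alpha 0.025. An odds ratio of 1.3 is only about d = 0.145.

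This is the only power statement for the Aim 1 primary endpoints as they will finally be analysed. If it is believed, a non-significant result would be read as good evidence against an odds ratio of 1.3, which the trial has almost no ability to detect.

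**Working it through.** **Inputs from the documents.** Alpha 0.0125, 222/221 patients, 65% of controls at zero, odds ratio 1.3 and surgeon share 30% (preliminary data 5%) are from the SAP's modified power analysis. Two-sided testing is from the published protocol's power section. The layout is Table 1 of the published protocol: 40 surgeons, five sites, six waves, 8 surgeons crossing over per wave. Planned recruitment is 480/(40 × 6) = 2 patients per surgeon-wave; realised, 443/240 = 1.85.

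**Assumptions not in the documents.** The surgeon share is on the latent logistic scale for the logistic and ordinal models; the ordinal 35% splits equally between 1 and 2+ unless stated; patients are spread evenly or at random over surgeon-waves; there is no true secular trend.

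**1. The published power figures reproduce.** Linear stepped-wedge information with a surgeon intercept and 30 site-by-wave effects, 480 patients and a 5% share gives SE 0.134 SD. With z = 2.241 (alpha 0.025):
- d = 0.425: Φ(0.425/0.134 − 2.241) = 82.4% (published 82%)
- d = 0.5: 93.2% (published 93%)

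At a 30% share the same layout gives 84.5% and 94.4%. With 443 patients the SE is 0.135–0.142 over shares of 5%, 15% and 30%. Regret at 0.23/0.46 = 0.5 SD and alpha 0.05 then has 94–96% power, consistent with the stated figure of over 91%.

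**2. The stated effect.**
- Intervention proportion = 1.3 × 0.35 / (0.65 + 1.3 × 0.35) = 0.455/1.105 = 0.412
- Difference = 0.062
- Latent d = ln(1.3) × √3/π = 0.262 × 0.551 = 0.145

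**3. Most favourable case: no clustering, no period effects.** z = 2.498 for two-sided 0.0125.
- Binary: null SE 0.04614, alternative SE 0.04605. Power = Φ[(0.06176 − 2.498 × 0.04614)/0.04605] = Φ(−1.16) = **12.3%**.
- Ordinal, proportional odds: mean category proportions 0.619/0.185/0.196. Information = (1 − Σp³)/3 ÷ (1/222 + 1/221) = 27.6. Power = Φ(0.262 × √27.6 − 2.498) = Φ(−1.12) = **13.2%**. Splitting the upper 35% from 20/80 to 80/20 gives 12.9–13.2%.
- Looser alpha does not rescue the binary figure: 26.7% at two-sided 0.05 and 37.9% at one-sided 0.05.
- 85% power with individual randomisation would need about 1,543 patients per arm.

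**4. The stepped wedge with 443 patients, alpha 0.0125, odds ratio 1.3.**

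| Method | Binary | Ordinal |
|---|---|---|
| Linear information, risk-difference or latent-d scale | 5.5–7.7% | – |
| Planned mixed models, expected information, share 5% / 15% / 30% | 5.4 / 4.4 / 3.7% | 5.7 / 4.7 / 4.1% |
| Simulation, 400 runs, share 5% / 30% | 7.8 / 4.8% | 7.8 / 5.0% |
| Simulation, 1,000 runs, share 5% / 30% | 6.1 / 3.0% | 6.6 / 4.7% |

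The 1,000-run binary simulation under no effect (30% share) rejected in 1.1%, against the nominal 1.25%. Allowing up to 3 patients per surgeon-wave, as the SAP permits, leaves power at 3.6–5.4%.

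**5. Odds ratio needed (planned mixed models, share 5% / 15% / 30%).**
- 85% power, binary: 2.9 / 3.3 / 3.8
- 93% power, ordinal: 3.1 / 3.5 / 4.0

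**6. A possible source.** If 1.3 was entered as a log odds ratio, the odds ratio is e^1.3 = 3.67 (35% to 66%). At a 30% share the mixed models give 83% binary (simulations 84% and 85%) and 88–90% ordinal across splits (simulations 90% and 90.5%). A cruder information approximation gives about 94% and 96%. No single method returns both stated figures. The documents do not say this happened; it is an inference.

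**The case against.** The core cannot be rebutted: no choice of alpha, sidedness, surgeon share or effect scale that was tried brings an odds ratio of 1.3 near 85%. The fair objections concern the secondary figures and the consequence.

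- **The 4–6% rests on unstated inputs.** This is true. All methods together give 3–8%. The contradiction does not depend on it, because the ceiling without clustering is 12–13%.
- **The required odds ratio depends on method.** This stands. An information approximation with a latent-scale share gives about 2.7–3.1 for the binary endpoint. With an observed-scale share, power is 81% at 2.5 and 92% at 2.9. A fair overall range is 2.6–3.8, so 3.8 is not settled. Nothing in that range is near 1.3.
- **Whether a 30% share is the worst case depends on scale.** It is in the latent-scale logistic model, but in the linear model it gives more power than 5% or 15%.
- **The log odds ratio reading is speculative.** Agreed. It is a lead for the code check, and whether the 93% survives it depends on the method.
- **The regret and d = 0.425 figures are not errors.** Agreed; they serve only as contrasts.
- **Recruitment is complete, so no sample size turns on this, and the plan nowhere says a null result excludes 1.3.** True. That limits the consequence to interpretation, but the power statement for the primary endpoints remains false as written.

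**Conclusion.** The concern holds. At an odds ratio of 1.3 the design has at most 12–13% power per endpoint, and about 4–6% under the planned models (3–8% over all methods), against the stated 85% and over 93%. Either the effect size or the power is wrong. The 12–13% ceiling uses only the SAP's inputs and two-sided testing from the published protocol; the ordinal split barely moves it. The lower figures also rest on the Table 1 layout, a surgeon share of 5–30% and the listed assumptions. If the power figures are right, the effect they refer to is an odds ratio of roughly 3 to 4 under the planned mixed models, not a modest one. This must be corrected before the results are interpreted.

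**What to change.** 1. Check the power code and correct whichever number is wrong. If 1.3 is a log odds ratio, say so, state the odds ratio of about 3.67, and recheck both the 85% and the 93%. If an odds ratio of 1.3 is meant, state the power at that value.
2. State the odds ratio detectable with 85% power for surgeon shares of 5% to 30% under the planned logistic and ordinal mixed models. Give the method, the scale of the surgeon share, the assumed split between 1 and 2+, and the patients per surgeon-wave.
3. Remove the statement that power remains robust for Aim 1 unless the corrected figures support it.
4. Report confidence intervals for the four odds ratios, and do not read a non-significant result as excluding 1.3.

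The cost is a rerun of the power code and SAP wording. The stated power or effect size becomes less favourable. No extra patients are needed, and alpha, models and endpoints do not change.
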